8.1.2. Temporary Interruption (Withholding) of Study Treatment

Some possible reasons for temporarily withholding the investigational product include (but are not limited to):

- Patient develops a clinically important intestinal or extraintestinal infection during the study, including latent tuberculosis infection (LTBI).
- Patient requires major surgery (resume administration of the investigational product only after adequate wound healing).
- Patient develops a confirmed absolute neutrophil count $<1 \times 10^9/L$ ($<1 \times 10^3/\mu L$ or <1 GI/L) (2 assessments below this threshold).
- Patient develops absolute lymphocyte count <500 cells/ μL ($<0.5 \times 10^3/\mu L$ or <0.50 GI/L). Azathioprine, 6-MP or methotrexate must be discontinued, if applicable, for a confirmed absolute lymphocyte count $<0.5 \times 10^3/\mu L$ (2 assessments below this threshold). The hematology must be repeated in 2 weeks. If the absolute lymphocyte count remains $<0.5 \times 10^3/\mu L$, the hematology will be repeated again in 2 weeks (that is, prior to the next dose of study drug). If the absolute lymphocyte count remains $<0.5 \times 10^3/\mu L$, the next dose of study drug will not be administered. The hematology will be repeated again in 2 weeks. If the absolute lymphocyte count remains $<0.5 \times 10^3/\mu L$, study drug will be permanently discontinued. White blood cell and lymphocyte counts will be followed for these patients until they return to an acceptable level.

Cases that may merit temporary withholding of the study treatment will be discussed with the medical monitor. The medical monitor, in consultation with the investigator, will determine when it is appropriate to recommence study treatment.

8.1.3. Discontinuation of Inadvertently Enrolled Patients

If the sponsor or investigator identify a patient who did not meet enrollment criteria and was inadvertently enrolled, then the patient should be discontinued from study treatment unless there are extenuating circumstances that make it medically necessary for the patient to continue on study treatment. If the investigator and the sponsor agree it is medically appropriate to continue on study treatment, the investigator must obtain documented approval from the sponsor to allow the inadvertently enrolled patient to continue in the study. Patients who are discontinued from study treatment should have safety follow-up as outlined in Section 2 (Schedule of Activities), Section 9.2 (Adverse Events), and Section 9.4 (Safety) of the protocol.

8.2. Discontinuation from the Study

Patients will be discontinued in the following circumstances:

- Enrollment in any other clinical study involving an investigational product or enrollment in any other type of medical research judged not to be scientifically or medically compatible with this study
- Participation in the study needs to be stopped for medical, safety, regulatory, or other reasons consistent with applicable laws, regulations, and good clinical practice
- Investigator decision
 - The investigator decides that the patient should be discontinued from the study
 - If the patient, for any reason, requires treatment with another therapeutic agent that has been demonstrated to be effective for treatment of the study indication, discontinuation from the study occurs prior to introduction of the new agent
- Patient decision
 - The patient requests to be discontinued from the study

Patients discontinuing from the study prematurely for any reason should complete AE and other safety follow-up per Section 2 (Schedule of Activities), Section 9.2 (Adverse Events), and Section 9.4 (Safety) of this protocol.

8.3. Lost to Follow-Up

A patient will be considered lost to follow-up if he or she repeatedly fails to return for scheduled visits and is unable to be contacted by the study site. Site personnel are expected to make diligent attempts to contact patients who fail to return for a scheduled visit or were otherwise unable to be followed up by the site.

9. Study Assessments and Procedures

Section 2 lists the Schedule of Activities, with the study procedures and their timing (including tolerance limits for timing).

[Appendix 2](#) lists the laboratory tests that will be performed for this study.

Unless otherwise stated in the subsections below, all samples collected for specified laboratory tests will be destroyed within 60 days of receipt of confirmed test results. Certain samples may be retained for a longer period, if necessary, to comply with applicable laws, regulations, or laboratory certification standards.

9.1. Efficacy Assessments

Table AMBG.9.1. Endpoint Definitions in Study AMBG

Endpoint	Definition
Clinical remission	
 Stool frequency (SF) subscore = 0, or SF = 1 with a ≥ 1-point decrease from induction baseline, and Rectal bleeding (RB) subscore = 0; and Endoscopic subscore (ES) = 0 or 1 (excluding friability)
Clinical remission (using a more stringent ES)	
 SF subscore = 0, or SF = 1 with a ≥ 1-point decrease from induction baseline, and RB subscore = 0; and ES = 0
Clinical response	
 A decrease in the modified Mayo score (MMS) of ≥ 2 points and $\geq 30\%$ decrease from baseline, and A decrease of ≥ 1 point in the RB subscore from baseline or a RB score of 0 or 1
Corticosteroid-free remission without surgery at Week 40^a	
 Clinical remission at Week 40, and Symptomatic remission at Week 28, and No corticosteroid use for ≥ 12 weeks prior to Week 40
Endoscopic remission	
 ES = 0 or 1 (excluding friability)
Endoscopic response	
 A decrease in the ES of ≥ 1 point compared to baseline
Histologic remission	
 This definition will be specified in the SAP
Mucosal healing	
 Histologic remission as described in the SAP and endoscopic remission defined as ES = 0 or 1 (excluding friability)
Symptomatic remission	
 SF = 0, or SF = 1 with a ≥ 1-point decrease from induction baseline, and RB = 0
Stable maintenance of symptomatic remission^b	
 Symptomatic remission for at least 7 out of 9 visits from Week 4 to Week 36 Symptomatic in remission at Week 40
Bowel movement urgency improvement	
 The definition will be specified in the study SAP

Abbreviations: ES = endoscopic subscore; MMS = modified Mayo score; RB = rectal bleeding; SAP = statistical analysis plan; SF = stool frequency.

^a Among patients induced into clinical response with mirikizumab during the induction study and who were receiving corticosteroids at induction baseline.

^b Among patients in symptomatic remission at Week 12 of Study AMAN.

9.1.1. Primary Efficacy Assessments

9.1.1.1. Primary Endpoint

The primary endpoint is **clinical remission** at Week 40, among patients induced into clinical response with mirikizumab induction treatment (Study AMAN). Clinical remission is based on the MMS and is defined in [Table AMBG.9.1](#).

9.1.1.2. Mayo Score

This study utilizes components of the Mayo Score (Schroeder et al. 1987) to assess UC disease activity for the primary and major secondary endpoints (see [Appendix 6](#)). **Complete and accurate recording of the Mayo SF and RB subscores by patients in their daily electronic diary is necessary for the success of the study.** Adequate bowel preparation and an endoscopy with adequate visualization of the mucosa will enable calculation of the Mayo ES.

The Mayo score is a composite instrument comprised of the following 4 subscores:

SF Subscore: The SF subscore is a patient-reported measure. This item reports the number of stools in a 24-hour period, relative to the normal number of stools for that patient in the same period, on a 4-point scale (see [Appendix 6](#)). **A stool is defined as a trip to the toilet when the patient has either a bowel movement, or passes blood alone, blood and mucus, or mucus only.** The absolute number of stools passed in a 24-hour period will be recorded by the patient in a daily electronic diary. The reference “normal” SF for that patient will be recorded electronically at the induction study screening visit. Study software will use the patient-reported daily SF and the reference normal SF to automatically calculate the Mayo SF subscore. The patient will record this in an electronic diary ([Appendix 7](#)). Further details on the analysis of diary items are contained in the statistical analysis plan (SAP).

Normal SF: The Normal SF is a patient-reported measure. This item reports the number of stools in a 24-hour period when the patient was in remission or, if the patient has never achieved remission, the reported SF before initial onset of signs and symptoms of UC. Remission refers to a period of time since being diagnosed with UC when the patient is not experiencing any signs or symptoms relating to UC. This period of time may last a few weeks or a few months or may even last several years. The patient will record this electronically as source data in the tablet device at the screening study visit of Study AMAN.

Rectal Bleeding (RB): The RB subscore is a patient-reported measure. This item reports the most severe amount of blood passed with stool for a given day, on a 4-point scale (see [Appendix 6](#)). The patient will record this in a daily electronic diary ([Appendix 7](#)). Further details on the analysis of diary items are contained in the SAP.

Endoscopic Subscore (ES): The ES is a physician-reported measure that reports the worst appearance of the mucosa on flexible sigmoidoscopy or colonoscopy, on a 4-point scale (see [Appendix 6](#)). Determination of the ES is further detailed in Section 9.1.1.3. Consistent with current clinical practice and regulatory advice, this study excludes friability from the definition of an ES of 1.

Physician’s Global Assessment (PGA): The Physician’s Global Assessment (PGA) is a physician-reported measure that summarizes the investigator’s assessment of the patient’s UC disease activity on a 4-point scale (see [Appendix 6](#)). The investigator will record the PGA electronically as source data in the tablet device at appropriate study visits. Consistent with regulatory guidance, the PGA will not be used for efficacy assessment in this study.

Each subscore is scored on a 4-point scale, ranging from 0 to 3. The MMS is a 9-point score, calculated by combining the SF, RB, and ES sub-scores. The PGA is collected in this study to facilitate historical comparisons of study data.

9.1.1.3. Endoscopy

Endoscopy will be used to determine the Mayo ES at the time points described in the Schedule of Activities (Section 2).

Flexible sigmoidoscopy is the standard endoscopic procedure for assessment of endoscopic disease activity in this study. However, colonoscopy can be performed instead of flexible sigmoidoscopy within this study in order to surveil for dysplasia, screen for colorectal cancer (see Inclusion Criterion [5]), or for other clinically indicated reasons, in the judgement of the investigator and after discussion with the medical monitor as appropriate.

Endoscopic disease activity assessed at Week 12 of Study AMAN will serve as the baseline assessment of endoscopic disease activity in Study AMBG.

In patients who enter Study AMBG in clinical response or clinical remission, endoscopy will be performed at Week 40, ETV, UV, or if LOR is suspected in these patients based on SF/RB scores, endoscopy can be performed at or after Week 12 to confirm secondary LOR. Secondary LOR must be confirmed endoscopically before rescue mirikizumab IV induction dosing is initiated. If endoscopy does not confirm secondary LOR, patients are encouraged to continue study drug dosing. If study drug dosing is continued, an additional endoscopy would be performed at Week 40, ETV, or UV.

In patients who enter Study AMBG as induction study nonresponders, endoscopy will be performed at Week 12, following extended mirikizumab IV induction. An additional endoscopy will be performed at Week 40, ETV, or UV. Patients who plan to continue in the long term extension study AMAP and who require an annual surveillance colonoscopy to remain up-to-date in screening for colorectal cancer (see Inclusion Criterion [5]), will undergo colonoscopy as the endoscopy method at Week 40.

If a patient becomes pregnant during the study, no additional endoscopies will be performed.

If a patient undergoes early termination soon after baseline, loss of response, or at the end of extended induction endoscopy, the need for ETV endoscopy should be discussed with the medical monitor.

The endoscopy report and histopathology report (if biopsies are sent to a local histopathology laboratory) must be available in the source documents.

The endoscopist will be a licensed physician, who is qualified by education, training, and experience to perform colonoscopies. Investigators may delegate endoscopy to other members of the study team. However, all study staff performing endoscopy must receive training from the sponsor or designee in the determination and calculation of the Mayo ES. The site endoscopist will determine the Mayo ES at each endoscopy and it will be recorded in the eCRF.

All endoscopic procedures will be video recorded using a storage medium provided by the sponsor or designee. The video images will be sent for independent central reading. A detailed image review charter from the central reading laboratory will outline the standard study procedures used to capture and transmit video recordings of endoscopic procedures throughout the study, and the qualifications required of the central reader.

The central reader will determine centrally-read Mayo ES at each colonoscopy in a blinded manner, as detailed in the image review charter.

Disagreement between the site and the central read will be adjudicated by an additional blinded central reader, as detailed in the image review charter. The adjudicated Mayo ES will be provided to the sites from the central reader vendor.

9.1.1.4. Endoscopic Biopsies

Biopsies will be obtained at each endoscopy to support assessment of the histopathology endpoints in this study, and where permitted, for the assessment of exploratory biomarkers. These will be sent to the central study laboratory for processing. Histopathologic scoring of these biopsies will be performed by a blinded central reader. A detailed histopathology charter will outline the procedures to be used for specimen transfer, processing, slide preparation, and digitization of slides for histopathologic scoring. Centrally read histopathology results will not be made available to study sites.

9.1.2. Secondary Efficacy Assessments

9.1.2.1. Major Secondary Endpoints

The major secondary endpoints are as follows (see [Table AMBG.9.1](#) for definitions):

- Clinical **remission** at Week 40, among patients induced into clinical **remission** with mirikizumab at Week 12 of induction study (Study AMAN)
- Endoscopic remission at Week 40, among patients induced into clinical **response** with mirikizumab at Week 12 of the induction study
- Corticosteroid-free remission without surgery at Week 40, among patients induced into clinical **response** with mirikizumab at Week 12 of the induction study and were receiving corticosteroids at induction baseline
- Histologic remission at Week 40, among patients induced into clinical **response** with mirikizumab at Week 12 of induction study
- Stable maintenance of symptomatic remission, among patients induced into clinical **response** with mirikizumab and were in symptomatic remission at Week 12 of induction study
- Bowel movement urgency improvement among patients induced into clinical **response** with mirikizumab at Week 12 of induction study

9.1.2.1.1. Histopathology Scoring Instruments

The histopathology instruments that will be used for the evaluation of microscopic inflammation and histopathologic disease activity will be specified in the histopathology charter.

9.1.2.1.2. Patient Reported Outcome Instruments

The Urgency NRS (see [Appendix 7](#) for description) is a PRO instrument used to collect bowel movement urgency data in the patient eDiary. The Urgency NRS will be used to determine the secondary endpoint for bowel movement urgency improvement (see [Table AMBG.4.1](#) for definition).

9.1.2.2. Other Secondary Endpoints

Other secondary endpoints are found in [Table AMBG.4.1](#).

9.1.2.2.1. Physician Reported Instrument

The Ulcerative Colitis Endoscopic Index of Severity (UCEIS) is a physician reported instrument for measuring the endoscopic disease activity of UC on flexible sigmoidoscopy or colonoscopy, that includes 3 descriptors of vascular pattern, bleeding, and erosions/ulcerations (Arai et al. 2016; Ikeya et al. 2016; Tontini et al. 2014). Only blinded central reading of endoscopies will be used to determine the UCEIS score for each endoscopy.

9.1.2.2.2. PRO Instruments Used to Assess Secondary Endpoints

The following are additional PRO instruments collected using a patient electronic diary (eDiary). Please see [Appendix 7](#) for additional descriptions.

- Abdominal Pain Numeric Rating Scale (NRS)
- Fatigue NRS (collected at site visits until Visit 10 when collected via electronic diary)

The following are additional PRO instruments collected using a tablet device. Please see [Appendix 7](#) for additional descriptions.

- Inflammatory Bowel Disease Questionnaire (IBDQ)
- European Quality of Life 5-Dimension 5 Level (EQ-5D 5L)
- Medical Outcomes Study 36-Item Short Form Health Survey (SF-36) Version 2
- Work Productivity and Activity Impairment Questionnaire: Ulcerative Colitis (WPAI:UC)

9.1.3. Exploratory Endpoints

Exploratory endpoints are defined in the SAP.

9.1.3.1. Inflammatory Biomarkers

C-reactive protein (CRP): CRP is an acute phase protein expressed by hepatocytes in response to inflammatory cytokines, particularly IL-6, tumor necrosis factor, and IL-1 β (Sands 2015). C-reactive protein will be obtained at the time points described in the Schedule of Activities (Section 2). Investigators will be blinded to CRP results.

Fecal calprotectin: Fecal calprotectin is a complex consisting of the calcium-binding proteins S100A8 and S100A9 (Sands 2015). It is expressed by activated neutrophils (and to a lesser extent by macrophages and monocytes) and fecal levels correlate with the number of neutrophils in the gut. It is used as a biomarker of intestinal inflammation in clinical practice. Fecal calprotectin will be obtained at time points described in the Schedule of Activities (Section 2). Investigators will be blinded to fecal calprotectin results.

9.1.3.2. Extraintestinal Manifestations

Review of extraintestinal manifestations (EIMs) will be performed at the time points described in the Schedule of Activities (Section 2). If new events are reported or ongoing events change in severity, they are to be reported as AEs. Extraintestinal manifestations include, but are not limited to: uveitis, episcleritis, peripheral arthritis, dactylitis, enthesitis, sacroileitis, ankylosing

spondylitis, erythema nodosum, pyoderma gangrenosum, primary sclerosing cholangitis, and oral aphthous ulcers.

9.1.3.3. PRO Instruments Used to Assess Exploratory Endpoints

The Patient UC Symptom Diary is a set of 8 items that assess UC-related symptoms in the past 24 hours ([Appendix 7](#)). In addition to the SF, RB, abdominal pain, and urgency items mentioned above, the diary also includes items that asks the patient to report stool consistency, the frequency of night-time stools, and overall disease severity.

The following exploratory endpoints will be assessed via the electronic diary tool and/or at applicable study visits using the tablet device:

- Nocturnal Stool (collected at site visits until Visit 10 when collected via electronic diary)
- Patient's Global Rating of Severity (PGRS) (collected via electronic diary)
- Bristol Stool Scale (collected at site visits until Visit 10 when collected via electronic diary)

In addition to those exploratory endpoints assessed by the Symptom Diary, the PGRC will be administered at applicable study visits using the tablet device. Additional descriptions of these PRO instruments can be found in [Appendix 7](#).

9.1.4. Appropriateness of Assessments

The clinical safety parameters in this study are routine elements of clinical health assessment and Phase 3 drug development. The disease activity measurements are used in clinical practice and UC clinical trials.

9.2. Adverse Events

Investigators are responsible for monitoring the safety of patients who have entered this study and for alerting Lilly or its designee to any event that seems unusual, even if this event may be considered an unanticipated benefit to the patient.

The investigator is responsible for the appropriate medical care of patients during the study.

Investigators must document their review of each laboratory safety report.

The investigator remains responsible for following, through an appropriate health care option, AEs that are serious or otherwise medically important, considered related to the investigational product or the study, or that caused the patient to discontinue the investigational product before completing the study. The patient should be followed until the event resolves, stabilizes with appropriate diagnostic evaluation, or is reasonably explained. The frequency of follow-up evaluations of the AE is left to the discretion of the investigator.

Lack of drug effect is not an AE in clinical studies, because the purpose of the clinical study is to establish treatment effect.

After the informed consent form (ICF) is signed, study site personnel will record via eCRF the occurrence and nature of each patient's preexisting conditions, including clinically significant signs and symptoms of the disease under treatment in the study.

In addition, site personnel will record any change in the condition(s), including exacerbation of UC, and any new conditions as AEs.

Investigators should record their assessment of the potential relatedness of each AE to protocol procedure or investigational product via eCRF.

The investigator will interpret and document whether or not an AE has a reasonable possibility of being related to study treatment, study device, or a study procedure, taking into account the disease, concomitant treatment, or pathologies.

A "reasonable possibility" means that there is a cause and effect relationship between the investigational product, study device, and/or study procedure and the AE. The investigator answers yes/no when making this assessment.

Planned surgeries and nonsurgical interventions should not be reported as AEs unless the underlying medical condition has worsened during the course of the study.

If a patient's investigational product is discontinued as a result of an AE, study site personnel must report this to Lilly or its designee via eCRF, clarifying if possible, the circumstances leading to any dosage modifications, or discontinuations of treatment.

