Investigators are not obligated to actively seek AEs or SAEs in patients once they have discontinued and/or completed the study (the patient disposition eCRF has been completed). However, if the investigator learns of any SAE, including a death, at any time after a patient has been discharged from the study, and he/she considers the event reasonably possibly related to the study treatment or study participation, the investigator must promptly notify Lilly.

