9.2.1.1. Suspected Unexpected Serious Adverse Reactions

Suspected unexpected serious adverse reactions (SUSARs) are serious events that are not listed in the IB and that the investigator identifies as related to investigational product or procedure. United States 21 CFR 312.32 and European Union Clinical Trial Directive 2001/20/EC and the associated detailed guidances or national regulatory requirements in participating countries require the reporting of SUSARs. Lilly has procedures that will be followed for the identification, recording, and expedited reporting of SUSARs that are consistent with global regulations and the associated detailed guidances.

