10.3.4. Safety Analyses

Safety will be assessed by evaluating exposure, AE (for example, treatment-emergent AE [TEAE], SAE, treatment related AE, discontinuation due to AE), AESI (for example, infection, MACE, injection site event, hypersensitivity event, etc.), laboratory analytes, vital signs, ECGs, C-SSRS, etc.

Adverse events will be coded according to the Medical Dictionary for Regulatory Activities and summarized by system organ class, preferred term, severity, and relationship to investigational product. A TEAE is defined as an event that first occurred or worsened in severity after baseline, which is the on-study AE recorded at Week 12 in the induction study. For each event classification term, the number of patients experiencing a TEAE with that classification term will be tabulated.

The safety analyses for the main cohort will compare mirikizumab to placebo during the maintenance treatment. For other cohorts, the safety data will be summarized without treatment comparison.

The Fisher exact test will be used to perform the between-treatment group comparisons for AEs, discontinuations, and other categorical safety data. The change from baseline in continuous vital signs, physical characteristics, and other continuous safety variables, including laboratory variables, will be summarized by visit and treatment. The change from baseline to last observation value will be analyzed with the ANOVA model with baseline as a covariate. The last non-missing observation in the treatment period will be used as the last observation.

Shift tables for categorical safety analyses (for example, “high” or “low” laboratory results) will also be produced.

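### Section 9.2 defines a reasonable possibility of relatedness as the existence of causation, which risks under-classifying events wherever the investigator's causality answer is used

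*Protocol*

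**What the plan says.** Section 9.2 of the Protocol describes the causality assessment in four steps.

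- It opens with a general instruction: "Investigators should record their assessment of the potential relatedness of each AE".
- It then frames the question. The investigator judges "whether or not an AE has a reasonable possibility of being related to study treatment, study device, or a study procedure", taking account of the disease, concomitant treatment and other pathology.
- It defines the key term. A reasonable possibility "means that there is a cause and effect relationship between the investigational product, study device, and/or study procedure and the AE".
- It fixes the response format: "The investigator answers yes/no when making this assessment".

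Other sections rely on the answer. Section 9.2.1.1 describes SUSARs as "serious events that are not listed in the IB and that the investigator identifies as related to investigational product or procedure". Under Section 9.2.1, an investigator who learns of an SAE after the patient has left the study must notify the sponsor if "he/she considers the event reasonably possibly related to the study treatment or study participation". The same section makes notification of an SAE between consent and first dose depend on a similar judgement about study procedures. Section 10.3.4 has adverse events "summarized by system organ class, preferred term, severity, and relationship to investigational product".

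**The concern.** The question asks about a possibility, but the definition supplies a fact. It contains no qualifier such as *may* or *suggests*, and the yes/no format leaves no intermediate category. An investigator who thinks the product might have caused an event, but cannot say that it did, should answer yes under the term and no under its definition.

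Two things are at stake. First, events that the product may have caused can be recorded as unrelated and so miss the actions that depend on relatedness. Second, two sites can classify the same event differently according to whether they follow the term or its definition, which makes the relationship summaries hard to interpret.

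**Working it through.** No figure in the protocol depends on this sentence, so the check is a comparison of texts.

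**Step 1: the standard each place sets.**

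- Section 9.2, general instruction: potential relatedness. A possibility standard.
- Section 9.2, the question: a reasonable possibility. A possibility standard.
- Section 9.2, the definition: causation exists. An established-fact standard.
- Section 9.2.1, SAEs before first dose and SAEs after discharge: reasonably possibly related. A possibility standard.

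The definition stands alone. Nothing elsewhere in the protocol rewrites it. Appendix 10 also works by likelihood: it counts a systemic reaction unless another cause is plausible and more likely.

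**Step 2: what a literal no does at each place of use.** This step assumes that sites carry the Section 9.2 definition over to the related wording in the other sections.

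- *SUSARs (Section 9.2.1.1).* The definition names only the investigator's identification. A no takes the event outside that definition.
- *SAEs after discharge (Section 9.2.1).* Sites have no duty to seek these events, and notification depends on the causality judgement. A no can mean that the sponsor is never told.
- *SAEs between consent and first dose (Section 9.2.1).* A no on relatedness to a study procedure removes the notification requirement. The event is still recorded in the eCRF.
- *Follow-up (Section 9.2).* Events must be followed if they are serious or otherwise medically important, considered related, or led to discontinuation of the product. For an event that is none of the others, relatedness is the only trigger, and a no removes the duty.
- *Summaries (Section 10.3.4).* A no moves the event out of the related category. Treatment-related events are also a named safety measure there.

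**Step 3: what does not depend on the answer.**

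- After first dose, Section 9.2.1 requires any on-study SAE to reach the sponsor within 24 hours, with no causality condition.
- Section 10.3.4 tabulates TEAEs by classification term and compares adverse events between groups by the Fisher exact test. The comparison of all events does not use relatedness.

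**Step 4: size.** Let E be the number of events that an investigator considers possibly, but not demonstrably, caused by the product, device or procedure. Let f be the share of these judged by the literal definition. The number misclassified is f × E. The protocol gives neither quantity. With f between 0 (sites ignore the definition) and 1 (all apply it), the result lies between none and all of E. The sentence applies to everyone enrolled, planned at about 1044, and not only to the 313 + 157 = 470 patients expected in the randomised main cohort.

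**The case against.** The best defence is that the sentence is loose drafting that nobody would follow to the letter. Every other formulation uses a possibility standard, and Section 9.2 asks the investigator to weigh disease and concomitant treatment, which is a judgement of likelihood. That makes wide literal use less probable. It does not cure the text, because the sentence presents itself as the definition of the term.

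A reader might infer that possibly related serious events will therefore drop out of expedited reporting. The documents do not support that as a certain result. On-study SAEs after first dose reach the sponsor regardless of causality. Section 9.2.1.1 adds that "Lilly has procedures that will be followed for the identification, recording, and expedited reporting of SUSARs that are consistent with global regulations", and Section 3.3 shows the sponsor making its own judgement that hypersensitivity reactions were related to mirikizumab. Sections 9.4.6 and 10.3.8 provide aggregate safety review and a data monitoring committee with unblinded data. These safeguards stand, but they are partial. Section 9.2.1.1 does not say that the sponsor's causality judgement alone makes a case a SUSAR. The sponsor also cannot assess a post-discharge event of which it is not told, and none of the safeguards restores the follow-up duty or the relationship summaries.

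A reader might also infer that the problem comes from blinding: an investigator who does not know the arm can hardly ever affirm that the drug was the cause. That does not hold either. The question concerns the investigational product, a device or a procedure, and Appendix 1 defines investigational product to include placebo. The same sentence governs the open-label induction nonresponders and the open-label rescue patients described in Section 7.1. The defect lies in the wording and is the same with or without blinding.

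**Conclusion.** The concern holds as a risk of under-classification. The definition is stricter than the term it defines and conflicts with the neighbouring wording in Sections 9.2 and 9.2.1. Followed literally, it directs a no for events that the product may have caused but where causation is not established.

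The exposure is greatest for SAEs after discharge, where the answer decides whether the sponsor is told, and for SUSAR identification if Section 9.2.1.1 is read as resting on the investigator alone. It is smaller for pre-dose SAEs, for follow-up of events with no other trigger, and for the relationship summaries. The between-group comparison of all adverse events is untouched, as are the efficacy analyses. How many events would change cannot be derived from the protocol. The conclusion assumes that at least some sites apply the definition as written. The sentence should be corrected.

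**What to change.** Replace the defining sentence in Section 9.2 with: *A reasonable possibility means that there is evidence or a plausible argument to suggest that the investigational product, a study device or a study procedure may have caused the AE; certainty of causation is not required.* Use the same wording in the eCRF completion guide, so that sites meet one standard. It would also help to state in Section 9.2.1.1 whether the sponsor's own causality judgement can make a case a SUSAR.

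The cost is one sentence in an amendment (two with the SUSAR clarification) and a short item in site training. Slightly more events will be marked related in all groups. If the change comes after enrolment has begun, the safety summaries should say which definition applied when each event was assessed.
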